A reduction in pain score does not directly correlate with an improvement in a patients' experience of that pain. Minimally clinically important difference (MCID) is what minimal change in a pain VAS score would indicate a real change in a patients' pain intensity. A systematic review of 29 studies identified an absolute MCID ranging from 8mm to 40mm and could not conclude a single MCID value because of the variety of different methods used to calculate the MCID. The importance of making a comparison against a patients' baseline pain was recognised³⁰.

The authors are not aware of any studies that have evaluated the MCID in pain VAS score following soft tissue corticosteroid injection in the hand and wrist. A recent observational study assessed MCID in VAS score in 224 post-operative patients concluded a MCID in pain VAS score of 10mm³¹. Two different papers determine 14mm as the MCID in pain VAS score in treatment of rotator cuff disease and following shoulder arthroplasty^{32, 33}. A large prospective multicentre study determined the MCID in pain VAS score in those with knee osteoarthritis to be 19.9mm³⁴. This study was reference and a MCID of 20mm used to evaluate patient reported outcomes following arthroplasty surgery³⁵. A 20mm MCID has also been used in other studies evaluating post procedural pain³⁶, one of which was also investigating pain following soft tissue corticosteroid injections in the hand²². Therefore, for the purpose of this study a MCID of 20mm will be used.

Non-inferiority studies:

Non-inferiority studies are a one-sided test used to determine if a novel treatment is no worse than the standard treatment. It is designed to show that the novel treatment is no less than a pre-specified unimportant amount from the standard intervention. Equivalence studies are a two-sided test used to show a novel treatment is no worse or no better than the standard treatment. It is designed to show that the two treatments do not differ in either direction by more than a pre-specified unimportant amount. This pre-specific unimportant amount is the margin that defines the "zone of indifference" within which the interventions are considered equivalent or non-inferior. Non-inferiority studies are often used in therapeutic trials when a novel treatment offers additional benefits to the standard treatment and the aim is to show that is non-inferior^{37,38}.

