In this instance the standard treatment is considered as a corticosteroid co-administered with local anaesthetic and the novel treatment corticosteroid alone. The hypothesis is that the pain at 1-hour post injection of corticosteroid alone is no worse than (not inferior to) the pain following a corticosteroid injection co-administered with local anaesthetic. The benefits of injecting corticosteroid alone, if the post injection pain was not inferior to co-administering it with local anaesthetic includes; stopping unnecessary administration of medication and reducing treatment time and cost. The zone of indifference has been set at <20mm, which has been determined from a MCID of 20mm a value below which it has been shown that there is no difference in pain experienced by the patient.

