2. STUDY OBJECTIVES

The primary objective:

Investigate whether there is a difference in pain VAS scores at 1-hour after a corticosteroid injection for trigger finger, de Quervains tenosynovitis or carpal tunnel syndrome co-administered with or without local anaesthetic.

The secondary objectives:

i) Investigate whether there is a difference in pain VAS scores during the 24-hours after a corticosteroid injection for trigger finger, de Quervains tenosynovitis or carpal tunnel syndrome co-administered with or without local anaesthetic.

ii) Investigate whether there is a difference in the pain VAS scores at the time of the corticosteroid injection for trigger finger, de Quervains tenosynovitis or carpal tunnel syndrome co-administered with or without local anaesthetic.

[figure not shown]
iii) Investigate the difference in the additional analgesia required and in the functional use of the hand during the first 3 hours following a corticosteroid injection for trigger finger, de Quervains tenosynovitis or carpal tunnel syndrome co-administered with or without local anaesthetic.

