7. STATISTICS AND DATA ANALYSIS

7.1 DESCRIPTION OF STATISTICAL METHODS

The primary objective;

Investigate whether there is a difference in pain VAS scores at 1-hour after a corticosteroid injection for trigger finger, de Quervains tenosynovitis or carpal tunnel syndrome administered with or without local anaesthetic.

Primary outcome measure of primary objective:

1a) A analysis of the mean change in pain VAS score between 1-hour post injection and baseline pre-injection will be performed. The primary intention will be the use of parametric tests

(Unpaired Students T-test) dependent upon the assessment of score distribution (skewness and kurtosis). Non-parametric testing will be employed if the mean distribution fails tests of normality.

Secondary outcome measures of primary objective:

1b) The effect size at 1-hour post injection will be calculated to measure the significance of the difference between the study and control group.

Mean score at 1-hour in corticosteroid alone group	-	Mean score at 1-hour in corticosteroid and LA group
Standard deviation		

The objectives;

i) Additional sensitivity analysis will be conducted to investigate whether there is a difference in pain VAS scores during the 24-hours after a corticosteroid injection for trigger finger, de Quervains tenosynovitis or carpal tunnel syndrome administered with or without local anaesthetic.

Outcome measure: The cumulative pain in the 24-hour period in both groups will be calculated by using the area under the curve. Multilevel linear regression analysis will be conducted to compare 24 hour pain VAS with injection intervention nested in patient condition.

ii) Additional sensitivity analysis will be conducted to investigate whether there is a difference in the pain VAS scores at the time of the corticosteroid injection for trigger finger, de Quervains tenosynovitis or carpal tunnel syndrome administered with or without local anaesthetic.

Outcome measure: the pain VAS scores in each group at the time of the injection. Multilevel linear regression analysis will be conducted to compare pain VAS with injection intervention nested in patient condition.

iii) Investigate the difference in the additional analgesia required and in the functional use of the hand during the first 3 hours following a corticosteroid injection for trigger finger, de Quervains tenosynovitis or carpal tunnel syndrome administered with or without local anaesthetic.

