7.2 THE NUMBER OF PARTICIPANTS

Minimally clinical important difference of 20mm will be used as the clinically admissible margin of non-inferiority. From previous studies, it is assumed to use a standard deviation of 25mm and with a 95% power calculations have determined a required sample size of 41 per study arm, when including a 20% fall out rate a total sample size of 100 patients will be required²².

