7.3 THE LEVEL OF STATISTICAL SIGNIFICANCE

. All statistical testing was done at the two-sided 5% significance level, and 95% CIs with Stata 14.2.

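### A non-inferiority trial with a 20 mm margin has a primary analysis that tests for a difference, and no rule ties the result to 20 mm

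*Combined protocol and SAP*

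**What the plan says.** The design side is consistent. The title, the aim and the hypotheses in Sections 1.1 and 1.2 all describe non-inferiority of corticosteroid alone to corticosteroid plus local anaesthetic at 1 hour. Section 1.1 explains the framework: "Non-inferiority studies are a one-sided test used to determine if a novel treatment is no worse than the standard treatment". It then fixes the margin: "The zone of indifference has been set at <20mm". Section 7.2 sizes the trial on it: "Minimally clinical important difference of 20mm will be used as the clinically admissible margin of non-inferiority".

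The analysis side reads differently.

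- The primary objective (Section 2, repeated in Section 7.1) is: "Investigate whether there is a difference in pain VAS scores at 1-hour after a corticosteroid injection".
- Item 1a of Section 7.1 states: "A analysis of the mean change in pain VAS score between 1-hour post injection and baseline pre-injection will be performed". The test is given as "Unpaired Students T-test) dependent upon the assessment of score distribution (skewness and kurtosis", and no null value is stated.
- The fallback is: "Non-parametric testing will be employed if the mean distribution fails tests of normality". No test is named.
- Item 1b adds a standardised effect size, without reference to the margin.
- Section 7.3 states: "All statistical testing was done at the two-sided 5% significance level, and 95% CIs with Stata 14.2".

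Nothing in Sections 7.1 to 7.7 says what result would establish non-inferiority.

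**The concern.** A t-test with its usual null asks whether the mean difference is zero. Non-inferiority asks whether a penalty of 20 mm or more can be excluded. The two questions can have different answers on the same data, and the text closest to the analysis points to the first.

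The fallback widens the gap. If it is a rank test, which is the natural reading, its p-value cannot be set against a margin in mm. It also no longer addresses the mean change that item 1a defines as the outcome.

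Two things are at stake. A non-significant result could be reported as showing that corticosteroid alone is no worse. And both the reading of the result and the choice of fallback test could be settled after the data are seen. The plan does not prescribe that misreading, but it does not rule it out.

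**Working it through.** **Inputs.** Margin 20 mm, SD 25 mm, power 95%, 41 per arm and 100 in total (Section 7.2); two-sided 5% and 95% CIs (Section 7.3); balanced allocation (Section 7.4). Assumptions not in the documents: a true difference of 0 for the sizing, normal data, the 25 mm SD applying to the change score, and SDs of 20, 30 and 35 mm to show a range.

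**Step 1: the plan's sample size.** n per arm = 2(SD/margin)²(z₁₋α + z₁₋β)².

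- One-sided 2.5%: 2(25/20)²(1.960 + 1.645)² = 40.6, so 41 per arm, as stated.
- One-sided 5%: 2(25/20)²(1.645 + 1.645)² = 33.8, so 34 per arm, which does not match.

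A two-sided 5% superiority test to detect 20 mm also gives 41, because the formula is the same. The number alone therefore does not show which design was sized; the wording of Section 7.2 does.

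**Step 2: interval width.** Half-width = t(0.975, 2n−2) × SD × √(2/n).

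- 41 per arm: SE = 25√(2/41) = 5.52 mm, half-width 10.99 mm.
- 50 per arm (100/2, no dropout): SE = 25√(2/50) = 5.00 mm, half-width 9.92 mm.

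**Step 3: where the two readings part.** Let d be the observed difference in mean change, corticosteroid alone minus corticosteroid plus local anaesthetic. The test against zero is non-significant when |d| is below the half-width. The upper 95% limit is below 20 mm when d is below 20 minus the half-width. With 41 per arm and an observed SD of 25 mm, these thresholds are 10.99 and 20 − 10.99 = 9.01 mm. An excess of 9.0 to 11.0 mm is therefore non-significant without showing non-inferiority. Such a zone exists only if the half-width exceeds 10 mm.

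**Step 4: error if p>0.05 were read as no worse.** This is the chance of a non-significant result when the true penalty is 20 mm, from the noncentral t distribution with noncentrality 20/SE. A confidence-limit rule has 2.5% in every row.

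| n per arm | SD (mm) | Half-width (mm) | 20 − half-width (mm) | P(p>0.05) at a true 20 mm |
|---|---|---|---|---|
| 41 | 25 (plan) | 10.99 | 9.01 | 5.3% |
| 50 | 25 (plan) | 9.92 | 10.08 | 2.3% |
| 41 | 20 (assumed) | 8.79 | 11.21 | 0.6% |
| 41 | 30 (assumed) | 13.19 | 6.81 | 15.3% |
| 41 | 35 (assumed) | 15.38 | 4.62 | 27.6% |

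At SD 20 mm the mismatch reverses: an observed 8.8 to 11.2 mm is significant and yet within the margin.

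**Step 5: how often the readings disagree.** In a simulation with 41 per arm, SD 25 mm and a true difference of 10 mm (200,000 runs), p>0.05 occurred in 57% of trials and non-inferiority was shown in 43%. In 14% the result was non-significant without showing non-inferiority. In 0.8% it was significantly worse yet non-inferior.

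**Step 6: power of the confidence-limit rule.** At SD 25 mm and a true difference of 0, exact power is 94.7% with 41 per arm and 97.7% with 50.

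No error rate is given for the non-parametric branch, because it depends on the unknown shape of the scores.

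**The case against.** The best defence is that the parts are all present. Section 1.1 describes the margin as bounding a zone within which treatments count as non-inferior and applies it to this trial with a direction and a figure. Section 7.2 repeats the margin, and Section 7.3 promises 95% CIs. Section 7.1 states no null of zero, and a two-sided 95% CI is the very interval a non-inferiority verdict would use, so the one-sided background and the two-sided level are compatible. On the t-test branch a careful analyst could reach the right verdict.

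That much stands. But the zone is general background and does not say whether the estimate or the confidence limit must lie inside it. The stated objective and test point to a comparison with zero, and the reader has to supply the trial's central decision rule.

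Some narrower points also stand. The error rates apply only under a misreading that the plan does not state. At the planned SD the zone is 2 mm wide, and it disappears with 50 evaluable per arm. The larger rates rest on SDs that the documents do not give. A difference that is significant but within the margin is no paradox; it is a mismatch only if the test against zero is taken as the verdict. A Hodges-Lehmann interval would also give a figure in mm, though for a location shift and not for the difference in means. A robust standard error mainly addresses unequal variances and does less for the skewness that triggers the switch, which favours the bootstrap.

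**Conclusion.** The concern holds and must be fixed. The test as written does not answer the trial's own hypothesis, and neither branch of the primary analysis has a stated criterion for non-inferiority.

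The numerical effect is modest at the planned values (5.3% against 2.5% with 41 per arm, nothing lost with 50) and grows if the SD exceeds 25 mm or numbers fall short. The severity does not rest on those rates. It rests on a confirmatory trial lacking a prespecified rule for its primary claim, with the choice of reading and of fallback test left open until after the data are seen. The sample size is not in error.

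**What to change.** - **Section 7.1, item 1a.** State that the primary analysis is the between-group difference (corticosteroid alone minus corticosteroid plus local anaesthetic) in mean VAS change from baseline to 1 hour, with a two-sided 95% CI, and that non-inferiority is concluded only if the upper limit is below 20 mm.
- **Fallback.** Replace the switch to non-parametric testing with one interval named in advance, preferably a bootstrap 95% CI, for the same mean difference and against the same 20 mm.
- **Primary objective** (study summary, Sections 2 and 7.1). Reword it as non-inferiority.
- **Section 7.3.** Add that the primary conclusion rests on this interval, equivalent to a one-sided 2.5% test, and keep the existing text for the secondary analyses. This also reconciles Section 7.3 with the one-sided description in Section 1.1.

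The cost is wording only. The endpoint stays, and 41 per arm already fits this rule. Section 3 keeps returned forms sealed until recruitment ends, so the rule can be fixed before any score on them is measured, provided they have not yet been opened; the documents do not give the trial's current status.

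### Section 7.1 lets a normality check on the outcome data choose the primary test, and the non-parametric branch is unnamed and has no stated link to the 20 mm margin

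*Combined protocol and SAP*

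**What the plan says.** Section 7.1, item 1a, defines the primary outcome on the millimetre scale: "A analysis of the mean change in pain VAS score between 1-hour post injection and baseline pre-injection will be performed". The intended test is an unpaired t-test, but it is made "dependent upon the assessment of score distribution (skewness and kurtosis"). The fallback is: "Non-parametric testing will be employed if the mean distribution fails tests of normality".

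Section 7.1 does not name the normality test, its cut-off, the distribution examined (each arm, pooled, or residuals) or the non-parametric method.

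Section 7.2 fixes the margin: "Minimally clinical important difference of 20mm will be used as the clinically admissible margin of non-inferiority". On the inputs, "it is assumed to use a standard deviation of 25mm and with a 95% power", it arrives at 41 per arm, and 100 in total after allowing for 20% loss. Section 7.3 adds: "All statistical testing was done at the two-sided 5% significance level, and 95% CIs with Stata 14.2".

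**The concern.** Two things go wrong together. First, the primary analysis is not fixed before the outcome data are seen, and the undefined check leaves the analyst several defensible routes. Second, the routes need not answer the same question. The t-test addresses the difference in mean change in mm, which is what the margin and sample size concern. A usual rank method addresses a location shift, meaning the typical difference between a patient in one arm and a patient in the other. The two agree when the arms differ only by a shift. They part when the arms differ in shape or spread.

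At stake is the trial's one primary conclusion. If a minority of steroid-alone patients had much more pain at 1 hour, the data would tend to fail the check, and the rank method would give those patients less weight than the mean does. The gap would also remain after adding a rule that the upper 95% limit must lie below 20 mm: the t branch would then be complete, but the switched branch would still have no specified estimate to set against 20 mm.

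**Working it through.** **1. What the sample size is for.** Inputs from sections 7.2 and 7.3: margin 20 mm, SD 25 mm, power 95%, two-sided 5% (one-sided 2.5%). Assumed: true difference 0. The formula for a difference in means is n per arm = 2 × (z for alpha + z for power)² × SD² / margin².

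- One-sided 2.5%: 2 × (1.960 + 1.645)² × 625 / 400 = 40.6, rounded up to 41. This reproduces the plan.
- One-sided 5%: 2 × (1.645 + 1.645)² × 625 / 400 = 33.8, rounded up to 34. This does not.

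So the trial is sized for a mean difference in mm with a two-sided 95% interval.

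**2. Why the target can move.** Suppose control changes are normal with SD s, and one third of steroid-alone patients have 60 mm extra. The mean difference is 60 / 3 = 20 mm, exactly on the margin. The Hodges-Lehmann target is the value m that solves (2/3) Φ(m / (s√2)) + (1/3) Φ((m − 60) / (s√2)) = 0.5.

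- s = 12: m = 11.4 mm
- s = 18: m = 15.6 mm
- s = 25: m = 17.7 mm

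If instead half the arm has 40 mm extra, symmetry gives m = 20 mm, equal to the mean difference. The gap therefore depends on the shape of the data.

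**3. False non-inferiority at a true mean difference of 20 mm.** Assumptions not in the documents: 41 per arm analysed; a skewness-kurtosis test at 5% in each arm, with a switch if either fails; a Hodges-Lehmann 95% interval after a switch; non-inferiority claimed if the upper 95% limit is below 20 mm; scores not bounded at 0 and 100; 25 mm taken as the SD of the change score. The nominal rate is 2.5%. There were 20,000 trials per row, so the Monte Carlo standard error is about 0.1 percentage point near 2.5%.

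| Scenario (SD 25 mm unless stated) | Check fails | t always | With switch |
|---|---|---|---|
| Pure shift, normal | 11% | 2.7% | 2.8% |
| Pure shift, gamma-skewed | 91% | 2.5% | 2.6% |
| Pure shift, exponential | 99% | 2.4% | 2.6% |
| Steroid-alone gamma, skewed to high pain; control normal | 72% | 3.1% | 6.6% |
| Steroid-alone exponential, skewed to high pain; control normal | 91% | 3.5% | 8.9% |
| Both gamma; SD 30 steroid-alone, 20 control | 91% | 3.2% | 10.3% |
| One third of steroid-alone +60 mm, base SD 15 | 54% | 3.2% | 9.1% |
| Mirror: steroid-alone skewed to low pain; control normal | 72% | 2.0% | 1.2% |
| Mirror: both gamma; SD 20 steroid-alone, 30 control | 91% | 1.8% | 0.7% |

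**4. Sensitivity of the minority scenario to the base SD** (4,000 trials each; one third with +60 mm):

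| Base (control) SD | Steroid-alone SD = √(s² + 800) | t always | With switch |
|---|---|---|---|
| 12 mm | 30.7 mm | 2.8% | 22.0% |
| 18 mm | 33.5 mm | 2.8% | 4.6% |
| 25 mm | 37.7 mm | 2.8% | 3.3% |

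The 800 is (1/3)(2/3) × 60². With half the arm at +40 mm, both the t rule and the switch gave 2.4-2.7% at base SDs 12, 18 and 25, as step 2 predicts.

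**5. Bounded scores.** One run with VAS held to 0-100 mm (3,000 trials; assumed baseline mean 25 mm, SD 20 mm; 36% with +60 mm) gave 3.1% for t and 18.6% with the switch. Bounding does not by itself remove the effect.

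**The case against.** Several counter-arguments are sound.

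- **Direction.** A reader might infer that the switch generally favours a false claim of non-inferiority. It does not: there is no change under a pure shift and a fall in the mirror cases. The documents give no distribution data to say which case applies.
- **Size.** The 22% figure needs a control SD of 12 mm against a steroid-alone SD near 31 mm, and the plan assumes 25 mm. With a control SD of 25 mm the same scenario gives about 3%.
- **Plausibility.** Section 1.1 reports transient effects in 15-20% of carpal tunnel injections. At 20%, a mean difference of 20 mm would need 20 / 0.20 = 100 mm extra per affected patient, the whole scale. At +60 mm the mean difference would be 9-12 mm, inside the margin, so claiming non-inferiority would be correct. Section 1.1 also places flare after intra-articular injection beyond 90 minutes. In the other direction, it gives lidocaine an effect of 1 to 3 hours, so pain at 1 hour could well be distributed differently in the two arms.
- **The margin.** A reader might infer that 20 mm cannot be used after a switch. It can be compared with a Hodges-Lehmann limit in mm, but as a location shift. A bootstrap or permutation analysis of the mean is also non-parametric and would keep the mean difference. The gap is that none of these is specified.
- **Shared cause.** No rule comparing a limit with 20 mm is stated for the t-test either, so part of the missing link is a separate problem.
- **Mitigation.** Item 1b reports a standardised difference in 1-hour means whatever the check finds. That keeps a comparison of means in view, but not for the change score and not in mm with an interval.
- **Power.** Under a skewed pure shift with no true difference, the switch raises power: 94.3% to 98.2% (gamma) and 94.1% to 99.4% (exponential).

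These points limit the size of the concern and leave its direction open. They do not supply the missing specification, and they do not make the choice of test independent of the data.

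**Conclusion.** The concern stands as a specification fault. The primary estimand depends on the trial's own data, and the switched branch has no named method and no stated use of the 20 mm margin.

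Under the assumptions listed in the working, the switch leaves false non-inferiority at about 2.6% under a pure shift. It gives about 3-10% at SDs near the planned 25 mm when the steroid-alone arm is more skewed or spread towards high pain, about 22% in the extreme case, and about 1% in mirror cases. These are scenarios, not forecasts. The documents do not support saying that the trial will lean towards a false claim.

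The t-based interval stays at about 2-4% in every scenario, so the normality check is not needed to protect validity at this sample size. This should be fixed. It is a cheap improvement and leaves the sample size unchanged.

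**What to change.** In section 7.1, item 1a:

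- Delete the normality check and the switch.
- State that the single primary analysis, whatever the distribution, is the difference between arms in mean change in pain VAS at 1 hour, in mm. Use a t-based interval or an equivalent linear model, and compare its 95% CI with 20 mm.
- Name one sensitivity analysis, such as a Hodges-Lehmann estimate with its interval or a bootstrap interval for the mean difference, and state that it does not replace the primary result.

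The cost is wording only; 41 per arm stands. The downside is some loss of precision if the scores are very heavy-tailed, and the power gain under skewed pure shifts is given up. The change should be made before the assessment records are opened, which section 3 places after recruitment ends.

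### Outcome 1b offers a standardised effect size as a measure of significance; it cannot serve as one, and it leaves the mm scale of the 20 mm margin

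*Combined protocol and SAP*

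**What the plan says.** Section 7.1 gives two results under the primary objective.

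- **1a, the primary outcome:** "A analysis of the mean change in pain VAS score between 1-hour post injection and baseline pre-injection will be performed". The arms are compared by an unpaired t-test, or by a non-parametric test if normality fails.
- **1b, listed under** "Secondary outcome measures of primary objective": "The effect size at 1-hour post injection will be calculated to measure the significance of the difference between the study and control group". The printed formula starts from "Mean score at 1-hour in corticosteroid alone group", subtracts the corresponding mean in the corticosteroid plus local anaesthetic group, and divides by "Standard deviation". It does not say which arm, pooling or variable that SD refers to.

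Three other places bear on this. Section 2 states the primary objective as "Investigate whether there is a difference in pain VAS scores at 1-hour after a corticosteroid injection", with no mention of change from baseline; the hypothesis in sections 1.1 and 1.2 is also about pain at 1 hour. Section 7.2 sets the non-inferiority margin at 20 mm and assumes an SD of 25 mm. Section 7.3 puts all testing at the two-sided 5% level with 95% CIs.

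**The concern.** A mean difference over an SD describes size in SD units. Whether it is significant depends also on the number of patients, which the formula leaves out. The plan therefore gives the word significance one meaning in 7.3 and another in 1b, and a report that followed 1b literally could present a large or small effect size as a test result.

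The more practical loss is on the non-inferiority question. Section 7.1 never mentions the 20 mm margin, and for 1a it names a test but no reported estimate. 1b is the only between-arm effect estimate at 1 hour that 7.1 defines. It has no units and no CI of its own, its divisor is undefined, and it rests on a different variable from 1a. A reader who wants to know whether corticosteroid alone is less than 20 mm worse cannot learn it from 1b.

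**Working it through.** **Inputs.** From section 7.2: margin 20 mm, SD 25 mm, power 95%, 41 per arm, 100 in total. From section 7.3: two-sided 5%, so one-sided 2.5% for non-inferiority. The documents give no baseline SD and no correlation between baseline and 1-hour scores; values used for these are assumptions.

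**Step 1: the plan's own figure.** n per arm = 2 × (1.960 + 1.645)² × 25² / 20² = 40.6, rounded up to 41. This reproduces the plan. Nothing below changes the sample size.

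**Step 2: effect size and significance.** With a pooled SD, t = d × √(n/2) on 2n − 2 degrees of freedom. Take d = 0.40 throughout:

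| n per arm | t | two-sided p |
|---|---|---|
| 20 | 1.26 | 0.21 |
| 41 | 1.81 | 0.074 |
| 50 | 2.00 | 0.048 |
| 100 | 2.83 | 0.005 |

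The same d falls on either side of 5% at 41 per arm (the required number) and 50 per arm (half the recruitment target). At 41 per arm the 95% CI around d has a half-width of about 1.96 × √(2/41) = 0.43 near d = 0, and about 0.45 at d = 0.8. 1b does not ask for it.

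**Step 3: effect size and the margin.** Margin in SD units = 20 / SD: 20/20 = 1.00, 20/25 = 0.80, 20/30 = 0.67. A value of d = 0.5 means 10 mm at SD 20 and 15 mm at SD 30.

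**Step 4: the unnamed SD.** If the SD of the score is 25 mm at both times, the SD of the change is 25 × √(2(1 − r)). For assumed correlations r of 0.3, 0.5 and 0.7 this is 29.6, 25.0 and 19.4 mm. The same data can thus give different values of 1b, depending on the SD chosen.

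**Step 5: 1-hour scores against change scores.** Subtract the between-arm difference in mean change from the between-arm difference in mean 1-hour score. The 1-hour terms cancel and the between-arm difference in baseline means is left. This holds exactly when the same patients enter both. Under randomisation its expectation is zero, so both mm differences estimate the same quantity. Its standard error is baseline SD × √(2/41):

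| Assumed baseline SD (mm) | SE (mm) | P(more than 5 mm) | P(more than 10 mm) |
|---|---|---|---|
| 15 | 3.3 | 13% | 0.3% |
| 20 | 4.4 | 26% | 2.4% |
| 25 | 5.5 | 37% | 7% |
| 30 | 6.6 | 45% | 13% |

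Five mm is a quarter of the margin and 10 mm is half of it.

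**The case against.** The defence has real weight.

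- **1b decides nothing.** It is labelled secondary. The test belongs to 1a, and no threshold or margin is attached to 1b. A reader might infer that the trial could reach two conflicting non-inferiority verdicts, but the plan never asks for a verdict from 1b. This stands.
- **1b is not on a wrong variable.** A reader might infer that it misses the trial's primary quantity because 1a uses change. Yet 1-hour pain is what the objective and the hypothesis name, and it is 1a that departs from that wording. The remark in section 1.1 that comparison with "baseline pain was recognised" as important concerns how a minimal important difference is derived. It does not commit the plan to change scores. This stands too.
- **Disagreement with 1a is not in itself an error.** Both differences have the same expectation, and a secondary summary that differs from the primary one by chance is ordinary.
- **The word may be loose.** At a fixed n and with a pooled SD, d maps one-to-one to a t-statistic, and the formula is printed, so significance may simply mean magnitude. This softens the first complaint but does not remove it, because 7.3 uses the word for the 5% test. It also leaves the unnamed SD, the missing CI and the lost mm scale untouched.
- **The step 5 percentages are conditional.** They rest on an assumed baseline SD and on the same patients entering both analyses. Section 7.6 admits partially completed forms, so the two sets may differ.

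**Conclusion.** The point holds as a specification flaw of minor to moderate weight. As written, 1b gives neither a measure of significance nor a result that can be set against the 20 mm margin, and its divisor is undefined. These conclusions come from the text and from steps 2 and 3, and need no assumption about the data beyond illustrative values.

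The gap between the two mm differences is a matter of clarity in reporting. Its size ranges with the assumed baseline SD: more than 5 mm in about 13% to 45% of trials, and more than 10 mm in about 0.3% to 13%. No single figure in those ranges should be quoted as the plan's.

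The documents do not support a reading that the primary test, its power or the sample size is affected. The inconsistency beneath the mismatch lies between the stated objective (pain at 1 hour) and 1a (change from baseline).

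**What to change.** In section 7.1, replace 1b with the between-arm difference on the 1a outcome, corticosteroid alone minus corticosteroid plus local anaesthetic, in mm with its 95% CI, to be read against the 20 mm margin.

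If a standardised value is kept, compute it on that same outcome with the pooled SD of that outcome, give its 95% CI, label it descriptive, and delete the clause about measuring significance.

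Since this moves 1b away from the wording of the objective, mean 1-hour scores by arm can still be tabulated in mm, and a sentence should say that 1-hour pain is assessed as change from baseline.

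The cost is one formula and a few sentences. No extra data, visits or patients are needed.
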